Elastomeric power chains are resilient and latex-free orthodontic materials. They are made up of elastic material and consist of many connected rings. Each ring is engaged in a bracket to apply a force of 175-300 gm.

Plaque Index:¹⁷ (Annexure C)

Plaque index is a grading system used to assess the amount of plaque present at the gingival margins and helps in assessing oral health. It consists of four grades including, Grade 0, 1, 2 and 3. The increase in grade indicates the increased amount of plaque along the gingiva.

Gingival Index:²¹ (Annexure D)

Gingival index is a grading system that is used to assess the health of the gingiva. It consists of four grades including, Grade 0, 1, 2 and 3. The increase in grade indicates the compromised gingival health of the teeth.

Root Resorption:²²

Root resorption is a decrease in root length and width due to an inflammatory process. In orthodontics, during tooth movement, areas of necrosis develop called hyalinized areas, which result in root resorption. Periapical radiographs will be taken to assess the amount of root resorption by determining the length of the tooth from the cusp tip to the root apex.

Retraction Rate:¹⁶

The retraction rate of canine will be the distance travelled divided by the time interval needed for closure of spaces. It will be noted at four-time intervals i.e at the start of the canine retraction (T_0), after first month (T_1), second month (T_2) and third month follow-up (T_3).

Split-mouth Study:

A randomized controlled trial in which intervention and control are randomly allocated to the different quadrants in the oral cavity. In our study, Ni-Ti closed-coil springs and elastomeric power chains will be randomly allocated to the right and left quadrants of maxillary and mandibular arches.

MATERIAL & METHODS:

Study Design: A single center open labelled parallel split-mouth randomized controlled trialSettings: Dental clinics, Department of Surgery, The Aga Khan University Hospital, Karachi, Pakistan

Study Duration: One year after ethical review committee (ERC) approval **Sampling Technique:** Non-probability consecutive sampling

SAMPLE SIZE:

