The sample size was calculated using standard estimate where n = 8(CV2) /(PC2) [1+(1-PC)2] where PC is the proportionate change in means (PC = $(\mu 0 - \mu 1)/\mu 0$) and CV is the coefficient of variation (CV = $\sigma 0/\mu 0 = \sigma 1/\mu 1$). The study required a minimum sample size of 33 (N) patients in each group. With an inflation of 40% for an estimated loss to follow up/non-response rate, we will be including 46 (N) participants in this study, to achieve 80% power and to detect at least a 39% change in mean canine retraction rate values of 3.88 ± 2.66 mm and 5.45 ± 1.53 mm, with

elastomeric power chains and Ni-Ti closed-coil springs, respectively⁸ and 68% or less change in coefficient of variation at two-sided 5% level of significance.

SAMPLE SELECTION:

Inclusion Criteria:

- Patients aged between 13 40 years
- Patients undergoing fixed orthodontic treatment
- Patients requiring all first premolars extraction as part of orthodontic treatment
- Patients with all permanent teeth present and erupted (except for second and third molars)
- All patients who will sign the informed consent/assent form

Exclusion Criteria:

- Patients with systemic diseases that can affect tooth movements
- Patients with uncontrolled periodontal disease
- Patients with craniofacial syndromes
- Pregnant or lactating mothers
- Patients with bracket failures greater than three times per bracket during the study
- Patients on medications that can affect tooth movements
- Patients with Nickel allergy

DATA COLLECTION PROCEDURE:

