Adverse events will be reported to ERC within a week and any serious adverse event will be reported to the Department of surgery, sponsors, CTU, DRC, and ERC within 24 hours. All emergency side effects will be managed in the emergency department and the Department of Surgery will bear the charges.

STUDY GROUPS:

The patients will be screened using the inclusion and exclusion criteria by the co-investigator. Measurements for the canine root resorption, retraction rate, plaque accumulation and gingival health will be taken at T_0 , T_1 , T_2 and T_3 .

Intervention: Ni-Ti closed-coil springs **Control:** Elastomeric power chains

The participants will receive routine instructions for oral hygiene maintenance and care of the appliance verbally.

MATERIAL STORAGE:

Ni-ti closed-coil springs and Elastomeric power chains will be stored at room temperature at the Department of Surgery, Dental inventory.

DATA ANALYSIS:

Data will be entered and analyzed in SPSS for Windows (version 23.0, SPSS Inc. Chicago). Frequencies and proportions will be reported for categorical variables, such as gender. Shapiro-Wilk test will be used to check the normality of the data. Descriptive statistics, such as means and standard deviations for normally distributed or median and interquartile range (IQR) for non-normally distributed data will be reported for all baseline clinical factors. Paired t-test will be used for the pairwise comparison. For the two groups the mean/median scores for retraction rate, root resorption, gingival health and plague accumulation between the two groups will be assessed using Independent t-test for normally distributed data and Man-Whitney U test for non-normally distributed data. A *p*-value ≤ 0.05 at 95% confidence interval will be considered as statistically significant.

On achieving 50% of the sample size, an interim analysis will be run, if the results show that the given intervention is successful in significantly improving the rate of canine retraction in patients then further trial will be stopped and all the participants will be given the intervention.

FINANCE:

Departmental funds from the Department of Surgery and intramural grants will be applied for.

PUBLISHING POLICY/PLAN:

For publication the data will be utilized, and it could be presented in either national or worldwide forums.

DATA CONFIDENTIALITY:

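### The named tests cannot combine visits, so a three-month retraction comparison gains nothing from the T1 and T2 readings of patients without T3

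*Protocol*

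**What the plan says.** The primary objective (Objective) compares the two devices on retraction over three months. The visit schedule (Operational Definitions, Retraction Rate; repeated under Data Collection Procedure) has a reading at T0 and then "after first month (T_1), second month (T_2) and third month follow-up (T_3"). Each patient carries both devices, one per side, in both arches.

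Under Sample Size: "The study required a minimum sample size of 33 (N) patients in each group". The plan then enlarges this: "With an inflation of 40% for an estimated loss to follow up/non-response rate", "we will be including 46 (N) participants in this study". The allowance covers loss and non-response together, and no timing is given.

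Data Analysis states: "Paired t-test will be used for the pairwise comparison". It does not say whether sides or visits are paired. For the comparison of the two devices it names the independent t-test, or the Mann-Whitney U test if data are not normal. No other comparative method is named, and no visit is singled out for the primary comparison.

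**The concern.** Each of the three tests takes one number per unit. Applied to the three-month result, it uses only patients who have a T3 reading. Someone who moved through T1 and T2 and then left has informative readings on both sides, but these tests have no way to bring them into the T3 comparison. If the tests are run at each visit, each visit rests on a different set of patients.

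Two things are at stake. The first is precision, in a plan that makes a large allowance for loss. The second is bias. If leaving is related to movement already recorded, the patients left at T3 are a selected group. The protocol provides for removal during the study after repeated bracket failure or a reaction to the spring, and nobody is blinded, so selective loss cannot be ruled out.

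**Working it through.** **1. The plan's own figures.** With CV = 0.68 and PC = 0.39, the protocol's formula gives 8 × 0.68² / 0.39² × [1 + (1 − 0.39)²] = 8 × 0.4624 / 0.1521 × 1.3721 = 33.4, matching 33. The enrolled number is 33 × 1.40 = 46.2, matching 46. If 33 of 46 are seen at T3, the loss is 1 − 33/46 = 28%. If 40% are lost, 46 × 0.6 = 27.6 remain. Both cases are carried below.

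**2. Assumptions, because the documents give no figure.** One spring-minus-chain difference per patient (one arch, or the mean of two). Loss at random, spread evenly before T1, T2 and T3. T2-T3 correlation ρ of the device differences from 0.5 to 0.9. If cumulative distance is built from independent, equally variable monthly steps, ρ = √(2/3) = 0.82; measurement error would lower it.

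**3. Formula.** With n₁ ≥ n₂ ≥ n₃ patients at T1, T2 and T3, the completers' mean has variance σ²/n₃. The likelihood-based estimate has large-sample variance σ²(c₁/n₁ + c₂/n₂ + c₃/n₃). Here c₁ is the share of the T3 variance explained by T1, c₂ the further share explained by T2, and c₃ the remainder. For correlation decaying as ρ, ρ²: c₁ = ρ⁴, c₂ = ρ²(1 − ρ²), c₃ = 1 − ρ². For independent steps each share is 1/3.

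- 28% loss: n = 41.67, 37.33, 33.
- 40% loss: n = 39.87, 33.73, 27.6.

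Example, independent steps, 28% loss: (1/3)(1/41.67 + 1/37.33 + 1/33) = 0.02703. Completers: 1/33 = 0.03030. Ratio 1.12.

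| T2-T3 correlation | Ratio, 28% loss | Ratio, 40% loss |
|---|---|---|
| 0.5 | 1.04 | 1.06 |
| 0.6 | 1.06 | 1.09 |
| 0.82 (independent steps) | 1.12 | 1.19 |
| 0.9 | 1.18 | 1.30 |

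Simulations of 4,000 runs per case, which include the cost of estimating the regressions in a small sample, give about 1.03 to 1.19 at 28% loss and 1.04 to 1.27 at 40%, close to the formula.

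**4. In patients.** 28% loss: 33 × 0.03 = 1 to 33 × 0.19 = 6. 40% loss: 27.6 × 0.04 = 1 to 27.6 × 0.27 = 7.

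**5. Upper limit.** If every patient missing T3 had both T1 and T2, the effective number at 40% loss would be 46 / [(1 − R²)/0.6 + R²], where R² is the share of the T3 variance explained by T1 and T2. This gives 30.7, 34.5 and 40.6 for R² = 0.25, 0.5 and 0.8, against 27.6 completers. If patients leave before T1, nothing is recovered from them.

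**6. Power of a completers' paired t-test.** The planned difference is 5.45 − 3.88 = 1.57 mm. The SD of the difference is √(2.66² + 1.53² − 2r × 2.66 × 1.53), where r is the correlation between sides (not given): 3.07 mm at r = 0 and 2.31 mm at r = 0.5. From the noncentral t distribution, power at 28 and 33 patients is 74% and 81% at r = 0, and 93% and 97% at r = 0.5.

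**7. Bias, as an illustration only.** In a simulation with 28 to 40% loss before T3, where the log-odds of loss rise by 0.5 per SD of the T2 device difference, the completers' T3 mean was 1.17 to 1.32 mm against a true 1.57 mm. The likelihood estimate was 1.57 to 1.58 mm. The strength of that dependence is assumed, and this loss mechanism is missing at random by construction.

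**The case against.** A reader might infer that the plan discards the early data of everyone missing at T3. The protocol does not say so. It writes no T3-only or completers rule. Tests at T1 and T2 would use those readings at those visits, and a rate to the last attended visit is compatible with the definition of retraction rate. Rules for missing visits are commonly left to a statistical analysis plan, so their absence is not a fault here. A reader might also infer that 40% are expected to be gone by month three. The allowance includes non-response and has no timing, and a patient with no follow-up reading gives a model nothing to work with. Both points stand, and the claim is limited accordingly.

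The gain may also be small. At a correlation of 0.5 it is about one patient, and if the two sides are well correlated a completers' paired test has ample power for 1.57 mm. This stands too, and it is why the range is shown from its low end. Comparing an effective number of pairs with the plan's 33 would be loose, because 33 is a per-group, two-sample figure.

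On bias, a patient who leaves a split-mouth trial normally takes both sides along, so differential loss between devices is largely removed. What can remain is selection on the size of the device difference, and the model deals with that only under missing at random.

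None of this answers the central point: the tests that the protocol itself names cannot draw on T1 and T2 for a three-month comparison.

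**Conclusion.** The point holds as a mismatch between the stated schedule, the stated allowance for loss and the stated tests. It is a worthwhile improvement in efficiency and robustness, not evidence that the primary test will fail. The gain is roughly 1 to 7 patients, resting on the assumed even loss and correlations of 0.5 to 0.9. The upper half of the range needs correlations of about 0.82 or more. The documents do not support a claim that early data are thrown away by rule, nor that a mixed model removes bias whatever the reason for loss.

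**What to change.** For retraction, replace the separate tests with one mixed model for repeated measures:

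- **Outcome:** within-patient spring-minus-chain distance moved from T0, at T1, T2 and T3. State that this is distance over a fixed interval; dividing by that interval gives the rate, so the comparison is equivalent.
- **Terms:** visit as a factor, unstructured covariance across visits, and arch as a factor with both arches clustered within patient (or the two arches averaged per patient).
- **Patients:** all with at least one follow-up reading.
- **Primary result:** the T3 contrast, and only that.
- **Sensitivity:** the T3 completers' paired comparison, by t-test or signed-rank test.

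The cost is a few lines in the protocol or analysis plan and a somewhat more complex analysis, with no extra patients or visits. The model relies on approximate normality of the differences, so the signed-rank sensitivity analysis should stay. It also relies on missing at random, which is less demanding than assuming that completers are a random subset but still cannot be verified from the data.

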After obtaining an approval from the Ethical Review Committee and taking informed consent and informed assent from the parents and child respectively, (Annexure E, F and G), these patients will be recruited in the study as participants. Patients visiting the orthodontic clinic at the Aga Khan University Hospital Karachi will be included in this study. Detailed information regarding the study will be provided to the participants and they will be given the choice to either accept or refuse their inclusion in the study. After the extraction of all first premolars under local anesthesia, 0.018" stainless steel archwires will be inserted in the maxillary and mandibular arches. For canine retraction, Ni-Ti closed-coil springs and elastomeric power chains will be randomly allocated to the right and left quadrants of both arches. Radiographic measurement (root resorption) and clinical measurements (canine retraction, plaque accumulation and gingival health) will be

recorded at four points in time. First, at the start of the canine retraction (T_0), after first month (T_1), second month (T_2) and third month follow-up (T_3). Canine retraction rate will be recorded by using a 100 mm marked scale.¹⁶ Data will be collected on an organized study proforma (Annexure H).

Ethical Considerations:

This study will be carried out as per the guidelines of the World Medical Association's Declaration of Helsinki.²³ and the principles of Good Clinical Practice (GCP). Any modifications in the protocol will be re-submitted to the ERC. The study will be conducted in compliance with regulations and a copy of the final study protocol will be submitted to ERC. All the recorded data of patients will remain confidential. Access will be provided to no one except the investigators. Participants' names and identities will remain undisclosed; however, data may be seen by ERC or any local regulatory body. Data will be saved for 7 years as per GCP and institutional guidelines.

Randomization:

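### The stated between-device test for plaque, gingival health and root resorption makes no use of the T0 values the trial collects, which costs precision in the secondary results

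*Protocol*

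**What the plan says.** - **Collection.** Protocol, Study Groups: "Measurements for the canine root resorption, retraction rate, plaque accumulation and gingival health will be taken at T_0 , T_1 , T_2 and T_3". T0 is the start of canine retraction, so every secondary outcome has a pre-treatment value on the same tooth.
- **Between-device test.** Protocol, Data Analysis: the "mean/median scores for retraction rate, root resorption, gingival health and plague accumulation between the two groups will be assessed using Independent t-test" for normal data, and a Mann-Whitney U test otherwise. No baseline term or change from T0 is mentioned, and the visit to be compared is not named (taken below as T3).
- **Other use of T0.** Under the same heading, summary statistics "will be reported for all baseline clinical factors", which is description only. There is also one short sentence: "Paired t-test will be used for the pairwise comparison". It does not say what is paired.
- **Root resorption.** Protocol, Operational Definitions, describes resorption as a decrease, but periapical films are to "assess the amount of root resorption by determining the length of the tooth from the cusp tip to the root apex". No T0-minus-T3 variable is written down.
- **Outside this point.** Retraction rate is distance over time, so it is already a change.

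**The concern.** Two canines in the same mouth can differ before any force is applied: one may be longer, or one side may be brushed better. If such a difference persists, part of it reappears at T3 and enters the device comparison. The named tests have no means of removing it. A within-patient test would remove what the two sides share, but not a right-left difference already present at T0.

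The three affected outcomes make up the whole secondary objective, and the Rationale stresses harm to roots and periodontal health. No sample size is given for them. A less precise comparison than the data allow makes a non-significant result easier to misread as reassurance.

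**Working it through.** **The plan's own figure.** The Sample Size formula with CV = 0.68 and PC = 0.39 gives 8 × 0.68² / 0.39² × [1 + 0.61²] = 8 × 0.4624 / 0.1521 × 1.3721 = 33.37, against 33 stated. Then 33 × 1.40 = 46.2, against 46 stated. Both rest on retraction rate. The number 33 is used below only to set a scale.

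**Assumptions.** The documents give no SD or correlation for plaque, gingival index or tooth length. Take one canine per side, total variance 1 at each visit, split into patient (vp), stable side difference (vt) and visit error (ve).

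**Formulas.**
- SE used by the independent test: √(2/n).
- SE of the side-to-side paired comparison: √(2(vt + ve)/n).
- Correlation of the T0 and T3 side differences: r = vt/(vt + ve).
- Variance left after adjusting the T3 difference for the T0 difference: 1 − r².
- Correlation of T0 and T3 on a single tooth: rho = vp + vt.

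The independent and paired tests share one point estimate, the difference in means, and differ only in the SE. Adjusting for T0 changes the estimate as well.

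**Results, n = 33, with rho = 0.9 in every row.**

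| vp / vt / ve (assumed) | r | Independent SE | Paired SE | Paired + T0 SE | Variance left by T0 after pairing | Equivalent n multiplier |
|---|---|---|---|---|---|---|
| 0.7 / 0.2 / 0.1 | 0.67 | 0.246 | 0.135 | 0.101 | 0.56 | 1.8 |
| 0.8 / 0.1 / 0.1 | 0.50 | 0.246 | 0.110 | 0.095 | 0.75 | 1.33 |
| 0.9 / 0 / 0.1 | 0 | 0.246 | 0.078 | 0.078 | 1.00 | 1.0 |

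First row: √(2 × 0.3/33) = 0.135; 1 − 0.667² = 0.556; 0.135 × √0.556 = 0.101.

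**Chance imbalance.** With equal variances at T0 and T3, a T0 side difference of one SE moves the unadjusted T3 result by r SE: none at r = 0, half an SE at 0.5, two-thirds at 0.67.

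**Simulation check** (33 patients, 4,000 replicates, no device effect):

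| vp / vt / ve | r | Paired SE | Paired + T0 SE | Change-score SE |
|---|---|---|---|---|
| 0.5 / 0.2 / 0.3 | 0.40 | 0.174 | 0.162 | 0.189 |
| 0.3 / 0.3 / 0.4 | 0.43 | 0.205 | 0.190 | 0.222 |
| 0.6 / 0.3 / 0.1 | 0.75 | 0.156 | 0.106 | 0.111 |
| 0.5 / 0 / 0.5 | 0 | 0.173 | 0.175 | 0.247 |

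Mean estimates were within 0.005 of zero under all three analyses, so none is biased. With nothing to gain (last row), adjustment costs almost nothing. An unadjusted change score has variance 2(1 − r) times that of the paired T3 comparison, so it is worse whenever r is below 0.5.

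**The case against.** **Resorption may already mean a change.** The protocol calls it a decrease and compares resorption, not tooth length; nowhere does it announce a comparison of T3 lengths. On that reading T0 enters by subtraction. This partly stands. But resorption is also to be taken at T0, where no decrease can yet exist, so what is recorded there is length and the derived variable still has to be written down. The reading does not help plaque or gingival grades.

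**Randomisation deals with baseline.** A reader might infer that ignoring T0 biases the device comparison or invalidates the test. The documents do not support that. Sides are randomised, the unadjusted estimate is right on average, and a valid test's error rate already allows for chance T0 differences. What is lost is precision.

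**A paired t-test is named.** If it pairs T0 with follow-up within a device, it uses T0 but gives no between-device estimate. If it pairs side with side, it leaves T0 side differences in place. The sentence does not settle the point. That the independent test ignores the split-mouth pairing is a separate matter.

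**The gain could look far larger.** A reader might put the single-tooth correlation into 1 − rho²: at 0.9 this leaves 0.19, or 1/0.19 = 5.3 times as many patients. That figure should not be used. Most of it is patient-level variation that pairing already removes; in the first table rho is 0.9 throughout while the further gain runs from 1.8-fold to none.

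**Baseline adjustment belongs in an analysis plan.** Often it does, and one may exist. Here the protocol itself names tests that cannot carry a T0 term, so the choice is fixed rather than left open.

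**Conclusion.** The point holds as a modest one about efficiency in the secondary outcomes. T0 values are collected on every canine, and the stated between-device tests do not use them. Relative to a within-patient analysis, adjusting for T0 would lower the variance by nothing at r = 0, 25% at r = 0.5 and about 45% at r = 0.67. These values of r are assumptions, because the documents give none. The gain is largest where the two canines differ stably before treatment. Tooth length is a plausible case, but nothing in the protocol shows how large such differences are. The figures also assume one canine per side and equal variance at T0 and T3.

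**What to change.** - **Define the outcome.** State root resorption as T0 length minus T3 length for each canine, in mm.
- **Main secondary analysis.** For each secondary outcome, regress the within-patient Ni-Ti minus chain difference at T3 on the same difference at T0. Leave the T0 difference uncentred: the intercept is then the device effect at equal starting values, whereas centring would return the unadjusted mean. For resorption, using the difference in loss or in T3 length gives the same adjusted estimate apart from sign.
- **Two arches.** Each patient supplies an upper and a lower difference. Either average them per patient, or fit a model with device and arch as factors and patient as a random effect, entering the T0 side difference and the T0 patient mean separately. A single term for each canine's own T0 value mixes within- and between-patient slopes and is not the same analysis.
- **Ordinal grades.** For the 0-3 plaque and gingival grades, check the model fit and add a rank-based or ordinal sensitivity analysis, so that the protection the Mann-Whitney provision was meant to give is kept.

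The cost is slightly more analysis work and the model check for the grades. No new data, visits or patients are needed.

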Randomization will be used in the study to allot one of the two treatment methods used for canine retraction to each side of the mouth to minimize bias and to account for individual variability. By randomly assigning different retraction methods to each side of the mouth any individual-specific factors that may affect the treatment outcomes (oral hygiene habits, masticatory habits) are likely to be equally distributed across the treatment group. Block randomization will be performed to code the type of retraction method in this trial and to determine the sequence of its administration to each participant. This will be controlled by a research faculty member of the Section of Dentistry at AKUH.

Sequence Generation:

In this two-armed study, four-blocks, each with a block size of six-possible allocation sequences for treatment arms will be generated.

(1) AABB, (2) BBAA, (3) ABAB, (4) BABA, (5) ABBA, (6) BAAB

The blocks to be utilized and their order will be determined by the research faculty member using sealed envelopeTM online software.²⁴

Allocation Sequence Concealment:

After fulfilling the inclusion criteria and obtaining consent, the patient will be recruited in the study. During the recruitment of the participants in the trial, the sealed envelope for a participant will be opened by the enrolling team member and will be allotted an intervention according to the ascending order sequence already generated by the principal investigator who is also a biostatistician.

Enrollment:

After obtaining approval from the ERC (AKUH), each participant fulfilling the inclusion criteria for the study and consenting to participate in the trial will be assigned a participant ID.

Blinding:

The study investigators, patients recruited, and assessors will not be blinded during the trial. All the measurements will be recorded by the co-investigator on the study proforma (Annexure H).

POSSIBLE RISKS OR BENEFITS:

Nickel is a known allergen, though people with nickel allergy tolerate stainless steel brackets and wires quite satisfactorily.²⁵ However, in case of any adverse events such as allergic reaction to Ni-Ti closed-coil spring such as contact dermatitis, rash, bumps, redness or irritation of the skin or mucosa, its use will be stopped, and patient will be excluded from the study.

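### The comparison of the two devices is assigned to independent-samples tests, although every patient carries both devices

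*Protocol*

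**What the plan says.** Three sections of the protocol put both devices in the same mouth. Under Operational Definitions (Split-mouth Study), "Ni-Ti closed-coil springs and elastomeric power chains will be randomly allocated to the right and left quadrants of maxillary and mandibular arches". The Data Collection Procedure repeats that the devices "will be randomly allocated to the right and left quadrants of both arches". The Randomization section gives the reason: one method is allotted "to each side of the mouth to minimize bias and to account for individual variability".

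The Data Analysis section then turns to the device comparison. Retraction rate, root resorption, gingival index and plaque index "between the two groups will be assessed using Independent t-test for normally distributed data and Man-Whitney U test for non-normally distributed data". The sentence before it reads "Paired t-test will be used for the pairwise comparison" and names neither an outcome nor a contrast. No paired non-parametric test is named anywhere.

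The Sample Size section is also written for two separate groups: "The study required a minimum sample size of 33 (N) patients in each group". Its inputs are a "change in mean canine retraction rate values of 3.88 ± 2.66 mm and 5.45 ± 1.53 mm".

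**The concern.** The independent t-test and the Mann-Whitney U test treat the two sides of one mouth as if they belonged to two unrelated people. The design was chosen so that differences between patients cancel in the left-right comparison. The named tests put those differences back into the error term.

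The paired t-test sentence does not settle the matter. Under Study Groups, "Measurements for the canine root resorption, retraction rate, plaque accumulation and gingival health will be taken at" four time points, so the sentence could mean change over time within one device. If it does mean spring versus chain, the primary comparison has two incompatible tests and no rule for choosing between them. Even then, non-normal outcomes would have only the Mann-Whitney test. That matters because plaque and gingival health are graded 0 to 3 (Annexures C and D).

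At stake are the width of the confidence intervals and the chance of missing a real difference. The three secondary outcomes have no power calculation. For root resorption and gingival health, a false conclusion of no difference is the error to avoid.

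**Working it through.** **Inputs from the protocol (Sample Size).** Means 3.88 mm (chains) and 5.45 mm (springs), so the difference is 5.45 − 3.88 = 1.57 mm. SDs are s0 = 2.66 and s1 = 1.53 mm. Two-sided 5% level, 80% power, 33 patients before inflation and 46 after.

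**Assumed.** The within-patient correlation r is not given; 0, 0.2, 0.3, 0.5 and 0.7 are used. The 1.0 mm difference is illustrative.

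**The plan's own figure.** With CV = 0.68 and PC = 0.39, the protocol's formula gives 8 × 0.68² / 0.39² × [1 + (1 − 0.39)²] = 33.37, which agrees with the stated 33. Then 33 × 1.4 = 46.2, which agrees with 46. The formula is for two independent groups and has no correlation term.

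**Standard errors, one value per device per patient.**
- The unpaired test uses √[(s0² + s1²)/n] = √[(7.0756 + 2.3409)/33] = 0.534 mm, whatever r is.
- The correct SD of the within-patient difference is √(s0² + s1² − 2·r·s0·s1). At r = 0.5 this is √(9.4165 − 4.0698) = 2.312 mm, and 2.312/√33 = 0.403 mm.
- The ratio at r = 0.5 is 3.069/2.312 = 1.33.
- The 95% half-width is the t quantile times the SE, with 64 df unpaired and 32 df paired.

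Type I error and power come from 200,000 simulated trials of bivariate normal pairs. The pooled-variance t-test and the paired t-test were run on the same data. Where a cell has two figures, they are unpaired / paired.

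| r | 0 | 0.2 | 0.3 | 0.5 | 0.7 |
|---|---|---|---|---|---|
| SD of difference (mm) | 3.069 | 2.791 | 2.641 | 2.312 | 1.928 |
| SE, unpaired over paired | 1.00 | 1.10 | 1.16 | 1.33 | 1.59 |
| Type I error, unpaired (%) | 5.1 | 3.3 | 2.4 | 1.1 | 0.3 |
| 95% half-width, n = 33 (mm) | 1.07 / 1.09 | 1.07 / 0.99 | 1.07 / 0.94 | 1.07 / 0.82 | 1.07 / 0.68 |
| Power at 1.57 mm, n = 33 (%) | 82 / 81 | 85 / 88 | 86 / 91 | 89 / 97 | 92 / 99.5 |
| Power at 1.57 mm, n = 46 (%) | 93 / 93 | 95 / 96 | 95.5 / 98 | 97 / 99 | 99 / 100 |
| Power at 1.0 mm, n = 33 (%) | 45 / 44 | 45 / 52 | 45 / 56 | 44 / 67 | 43 / 82 |

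**Outcomes without a power calculation.** With equal SDs and 33 patients, the paired test has 80% power for 0.503 SDs of the difference, which is 0.503 × √[2(1 − r)] outcome SDs. That gives 0.71, 0.64, 0.60, 0.50 and 0.39 SD across the five values of r. The unpaired test needs 0.70, 0.68, 0.67, 0.64 and 0.61 SD (simulated).

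**Graded outcomes.** A check on simulated 0–3 grades at r = 0.5 shows the same pattern. Type I error was 1.2% for Mann-Whitney and 5.3% for Wilcoxon signed-rank. Power was 46% and 68% for one illustrative shift.

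**If upper and lower canines are separate rows (66 versus 66).** The protocol neither states nor excludes this. With equal SDs, the true variance of the device contrast divided by the variance the test assumes is 1 − (patient share) + (patient-by-treatment share). Assumed shares ran from 0.5/0 to 0/0.5, with 33 patients and 100,000 simulated trials. Type I error of the independent t-test then ran from 0.7% to 11.1% with equal SDs, and from 1.6% to 11.1% with SDs 2.66 and 1.53. It exceeds 5% when the patient-by-treatment share is the larger one. The paired test on arch-averaged differences stayed at 4.9% to 5.2% throughout.

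**The case against.** The strongest reply is that pairing is not absent from the section. A paired t-test is named one sentence earlier, and left versus right is a natural reading of it in a split-mouth trial. That reading is possible. The text does not support it over change over time, however, and it would leave the explicit assignment to independent tests in place beside it. The best case is then a contradiction about the primary comparison.

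The second reply is that the harm is modest. With one value per device, the estimate is unbiased, false positives do not rise, and power at 1.57 mm is at least 82% with 33 patients. All of this stands. The large power loss needs an r of about 0.5 or more and an effect below the planned one. At r = 0.2 and 1.0 mm the gap is only 45% versus 52%. Smaller effects are not far-fetched on the protocol's own evidence, though: its introduction cites an average advantage of 0.5 mm over 12 weeks. At 0.5 mm, r = 0.5 and 33 patients, both tests are weak, with power of 9% unpaired and 23% paired.

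Third, the inflated type I error depends on separate rows and on a particular variance structure. That is right. It is a possibility the wording leaves open, and the conclusion does not rest on it.

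Fourth, averaging over arches is one choice among several; a mixed model with a patient random effect and arch as a factor would also respect the pairing. This stands too. The essential point is a within-patient comparison.

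**Conclusion.** The concern holds. The protocol fixes a test for the device comparison that contradicts its own design, for all four outcomes. This is a stated rule, not a detail left to a statistical analysis plan, and it should be corrected before any comparative data are analysed.

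Its size depends on r, which the protocol does not give. Between r = 0.3 and 0.7 the standard error is 16% to 59% too large and type I error falls to 2.4% to 0.3%. The 95% half-width is 1.07 mm where 0.94 to 0.68 mm was attainable. At r = 0 nothing material is lost. The planned power for 1.57 mm is met either way, so the cost is in precision, in smaller retraction effects and in the secondary outcomes. The millimetre figures take the Sample Size SDs as applying to one value per device per patient; the SD of an arch-averaged value is not given. The finding covers only the spring-versus-chain contrast.

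**What to change.** In the Data Analysis section, remove the independent t-test and Mann-Whitney U test for the device contrast. In their place, for each outcome, compute one spring-minus-chain difference per patient, averaged over the two arches. Test it with the paired t-test, or with the Wilcoxon signed-rank test if the differences are non-normal. The normality check should then be applied to those differences.

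State separately which contrast the existing paired t-test sentence covers, for example change over time within a device, and keep that analysis if it is intended.

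The cost is two or three sentences of protocol wording. No further patients or measurements are needed, and SPSS, the software already named, runs both paired tests.
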